6.3 Study Schema

Figure 4. NRX-101 for the Treatment of Suicidality in Bipolar Disorder

6.4 Study Population

The study analyses will be conducted in a GCP environment (ICH E6). All analyses will be pre-specified in a Statistical Analysis Plan (SAP) prior to beginning subject enrollment. The study will have prospectively defined study populations including separate evaluability rules for the ketamine treatment (Stage 1) and randomized treatment (Stage 2).

For Stage 1, the Intent-to-Treat (ITT) population will include all subjects who received the ketamine infusion and have the 24-hour post-infusion efficacy assessments. The Per-Protocol Population will include the subset of ITT subjects who were eligible, who had the 24-hour post-infusion efficacy assessments within 18 to 30 hours post the start of the initial infusion, and who had no major protocol violations. The Safety Population will include all subjects treated with ketamine who have any post-baseline safety data.

For Stage 2, the ITT population will include all subjects who received the randomized study treatment and have any post-baseline efficacy assessments. The Per-Protocol population will include the subset of ITT subjects who were eligible, who have any post-baseline efficacy assessments within 1 day of scheduled visits through Day 7 and within 2 days of scheduled visits through Day 42, and who had no major protocol violations. The Safety Population will include all subjects as treated with study treatment who have any post-baseline safety data through Day 70.

The ITT population will be used for the primary analyses. If <5% are to be excluded from the ITT population, then the analysis will not be performed for the PP population.

Every effort will be made to encourage subjects to comply with the procedures and the assessments involved in study. Non-compliance will be tracked. Protocol violations will be reviewed in real time; rules will be set for exclusions from the PP population.

A sufficient number (estimated to be 192 subjects) will be entered into Stage 1 in order to have 124 randomized subjects to complete Stage 2. IRB-approved written informed consent will be obtained from all subjects before any protocol-specified procedures are carried out. The subjects will be drawn from a sample of subjects with BD with suicidal ideation, diagnosed with the use of the MINI 7.0.2 for DSM 5. For entry into the study, all inclusion criteria must be met, and none of the exclusion criteria can be met.

7. SELECTION AND WITHDRAWAL OF SUBJECTS

Subjects must meet all of the inclusion and none of the exclusion criteria to be qualified to participate in this study.

7.1 Inclusion Criteria

1. Male or female, 18 to 65 years of age, inclusive, at screening.
2. Able to read, understand, and provide written, dated, informed consent prior to screening. Participants will be deemed likely to comply with study protocol and communicate with study personnel about AEs and other clinically important information.
3. Diagnosed with BD according to the criteria defined in the DSM-5. The diagnosis of BD will be made by a site psychiatrist and supported by the MINI 7.0.2. The diagnosis will be confirmed by remote, independent raters via teleconference between the screen visit and the baseline visit.
4. Suicidal ideation or behavior of sufficient severity to meet the requirements for a score of 4 or 5 on the C-SSRS.
5. A score equal to or greater than 20 on the MADRS items of the BISS.
6. In good general health, as ascertained by medical history, physical examination (PE) (including measurement of seated vital signs), clinical laboratory evaluations, and electrocardiogram (ECG).
7. If female, a status of non-childbearing potential or use of an acceptable form of birth control per the following specific criteria:
 - c. Non-childbearing potential (e.g., physiologically incapable of becoming pregnant, i.e., permanently sterilized [status post hysterectomy, bilateral tubal ligation], or is post-menopausal with her last menses at least one year prior to screening); or
 - d. Childbearing potential, and meets the following criteria:
 - iv. Childbearing potential, including women using any form of hormonal birth control, on hormone replacement therapy started prior to 12 months of amenorrhea, using an intrauterine device (IUD), having a monogamous relationship with a partner who has had a vasectomy, or is sexually abstinent.
 - v. Negative urinary pregnancy test at screening, confirmed by a negative urinary pregnancy test at randomization prior to receiving study treatment.
 - vi. Willing and able to continuously use one of the following methods of birth control during the course of the study, defined as those which result in a low failure rate (i.e., less than 1% per year) when used consistently and correctly: implants, injectable or patch hormonal contraception, oral contraceptives, IUD, double-barrier contraception, sexual abstinence. The form of birth control will be documented at screening and baseline.
8. Body mass index between 18-35 kg/m².

9. Concurrent psychotherapy will be allowed if the type (e.g., supportive, cognitive behavioral, insight-oriented) and frequency (e.g., weekly or monthly) of the therapy has been stable for at least three months prior to screening and if the type and frequency of the therapy is expected to remain stable during the course of the subject's participation in the study.
10. Concurrent hypnotic therapy (e.g., with zolpidem, zaleplon, melatonin, benzodiazepines or trazodone) will be allowed if the therapy has been stable for at least 4 weeks prior to screening and if it is expected to remain stable during the course of the subject's participation in the study. Subjects can also continue treatment with benzodiazepines used for anxiety if therapy has been stable for at least 4 weeks prior to screening and if it is expected to remain stable during the course of the subject's participation in the study.

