7.2 Exclusion Criteria

1. Female of childbearing potential who is not willing to use one of the specified forms of birth control during the study.
2. Female that is pregnant or breastfeeding.
3. Female with a positive pregnancy test at screening or baseline.
4. Current diagnosis of a substance use disorder (abuse or dependence, as defined by DSM-5, with the exception of nicotine dependence), at screening or within 6 months prior to screening.
5. Current Axis I disorder, diagnosed at screening with the use of the MINI 7.0.2, that is the primary focus of treatment and BD the secondary focus of treatment for the past 6 months or more.
6. History of schizophrenia or schizoaffective disorders, or any history of psychotic symptoms when not in acute bipolar mood episode.
7. History of anorexia nervosa, bulimia nervosa, or eating disorder not otherwise specified, within 5 years of screening.
8. Any Axis I or Axis II Disorder, which at screening is clinically predominant to their BD or has been predominant to their BD at any time within 6 months prior to screening.
9. Has dementia, delirium, amnestic, or any other cognitive disorder.
10. Has a clinically significant abnormality on the screening physical examination that might affect safety, study participation, or confound interpretation of study results according to the study clinician.
11. Participation in any clinical trial with an investigational drug or device within the past month or concurrent to study participation.
12. Current episode of:
 - i. Hypertension, Stage 1 as defined by a systolic blood pressure ≥ 140 mmHg or diastolic blood pressure ≥ 90 mmHg at screening on two of three measurements at least 15 minutes apart.

-
- j. Hypertension, Stage 1 as defined by a systolic blood pressure ≥ 155 mmHg or diastolic blood pressure ≥ 99 mmHg at the Baseline Visit (Visit 1) within 1.5 hours prior to ketamine infusion on two of three measurements at least 15 minutes apart.
 - k. Recent myocardial infarction (within one year) or a history of myocardial infarction.
 - l. Syncopal event within the past year.
 - m. Congestive heart failure (CHF) New York Heart Association Criteria $>$ Stage 2
 - n. Angina pectoris.
 - o. Heart rate < 50 or > 105 beats per minute at screening or randomization (Baseline Visit).
 - p. QTcF (Fridericia-corrected) ≥ 450 msec at screening or randomization (Baseline Visit).

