8.1.1 Study Visits and Assessments

A schedule of study visits and assessments is provided in Table 3 Schedule of Study ActivitiesTable 3

Table 3 **Schedule of Study Activities**

Assessment/Activity	Study Day	Screening Period 48 hrs	Stage 1			Stage 2										Follow Up /ET Day 70
			Ket. Dosing	4 hr	10 hr +2 hours	Day 1	Day 6	Day 7	Day 10	Day 14	Day 21	Day 28	Day 35	Day 42		
						24 hr post dose	+/- 1 day									
Visit Name/No.	Screen	Baseline			1	2	3	4	5	6	7	8	9	10		
Informed Consent		X														
MINI 7.0.2 DSM 5		X														
Demographics		X														
Medical History		X														
Psychiatric History		X														
Physical Exam		X								X				X		
Vital Signs		X	X	X		X		X	X	X	X	X	X	X		
ECG		X				X				X				X		
Concomitant Medications		X	X				X	X	X	X	X	X	X	X		
C-SSRS		X	X	X	X	X	X	X	X	X	X	X	X	X		
Phone Visit*					X		X									
Adverse Events		X	X	X	X	X	X	X	X	X	X	X	X	X		
CHRT—C, SR		X						X		X	X	X	X			
Remote Independent Rater Interview		X**														
CADSS			X	X												
BISS		X	X	X		X		X	X	X	X	X	X	X		
SIBQ			X	X		X		X	X	X	X	X	X	X		
Blood Draw for drug analyses		X				X***				X***				X***		
BARS			X					X	X	X	X	X	X	X		
BPRS			X	X												
PRISE			X	X		X		X	X	X	X	X	X	X		
Chemistry, CBC		X								X				X		
Urine Tox Screen		X								X				X		
Pregnancy Test (Urine)		X								X				X		
Ketamine Infusion			X													
Randomization						X										
Drug Dispensation & Pill Count						X		X		X	X	X	X	X		

*This phone visit should be performed by the site Principal Investigator, or Sub-Investigator. **The independent interview is performed remotely by telephone by independent raters.

***Blood draws for drug analyses 2 hours after the initial dose, prior to administration of NRX-101 on days 14 and 42, and 2 hours after administration of NRX-101 on day 42.

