8.2 Procedures

8.2.1 Laboratory/Diagnostic Procedures

Clinical laboratory safety testing will be conducted locally by the study site using CLIA-approved laboratories that have been audited by study personnel for compliance. Once the subject has signed the informed consent document, the urine pregnancy test will be performed at the Screen Visit, and Visits 5 and 9. ECGs will be measured at the Screen Visit, the Baseline Visit (at the 24-hour time point), and at Visits 5 and 9. Chemistry and complete blood count (CBC) will also be obtained at the Screen Visit, and at Visits 5 and 9. Weight, BMI, oral temperature, seated pulse and seated blood pressure (vital signs) will be recorded at each visit. At

Screen, and Visit 5 and 10, subjects will have a physical examination. The laboratory tests required are listed in Table 4, below.

Table 4 Laboratory Assessments

Laboratory Test	Frequency
CBC	Screen, Visits 5 and 9
Chemistry (Total bilirubin, AST, ALT, GGT, ALK Phosphatase, Creatine, BUN/Urea, Glucose, Uric Acid)	Screen, Visits 5 and 9
HbA1c (only for diabetics)	Screen
Pregnancy Test	Screen, Visits 5 and 9
Urine Toxicity Screen	Screen, Visits 5 and 9

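### The pregnancy test that inclusion 7 requires at randomisation, before study treatment, is missing from Table 3, Table 4 and section 8.2.1

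*Combined protocol and SAP*

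**What the plan says.** Section 7.1, inclusion 7, sets two tests for women of childbearing potential: "Negative urinary pregnancy test at screening, confirmed by a negative urinary pregnancy test at randomization prior to receiving study treatment". The synopsis repeats the requirement. Exclusion 3 in section 7.2 adds: "Female with a positive pregnancy test at screening or baseline". Section 7 makes the criteria binding: "Subjects must meet all of the inclusion and none of the exclusion criteria to be qualified to participate in this study".

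The scheduling text differs. Section 8.2.1 states that "the urine pregnancy test will be performed at the Screen Visit, and Visits 5 and 9". Table 4 gives the same three times. The urine pregnancy row of Table 3 has three marks, under Screening, Day 14 (Visit 5) and Day 42 (Visit 9). Section 8.1.6, which describes randomisation at the 24-hour visit, names the depression and suicidality response conditions but no pregnancy test.

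**The concern.** The eligibility section demands a test at randomisation, and every place that tells a site when to test leaves it out. Section 8.2.1 says when the test will be done, so a site that follows it could believe it has complied while omitting a required safety check.

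The protocol excludes pregnant women. If pregnancy occurs, section 12.1 stops study medication and calls for follow-up of the gestational outcome. A pregnancy missed at screening, or begun after it, could therefore be exposed to study drug until the Day 14 test. There is a lesser analytic consequence: the per-protocol set requires subjects to have been eligible and free of major violations, so missed tests could remove subjects from it.

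**Working it through.** **Schedule against criterion**

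| Source | Screening | Day 0, pre-infusion | Day 1, randomisation | Day 14 | Day 42 |
|---|---|---|---|---|---|
| Inclusion 7 | required | – | required | – | – |
| Section 8.2.1 | yes | no | no | yes | yes |
| Table 4 | yes | no | no | yes | yes |
| Table 3, by column position | yes | no | no | yes | yes |

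Tests scheduled at randomisation: 0. Tests required there: 1.

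The Table 3 reading can be checked against neighbouring rows. The Randomization row has its only mark at Day 1. The ECG row is marked at Screening, Day 1, Day 14 and Day 42, so it matches the pregnancy row plus a Day 1 mark. Exclusion 12p sets its QTcF limit "at screening or randomization (Baseline Visit", and there the schedule follows the criterion. The running text of 8.2.1 agrees with both tables, so a lost table mark does not explain the gap.

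**Age of the screening result at the first capsule**

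- Inputs: screening of up to 48 h (8.1.2); randomisation at 24 h post-infusion (8.1.6), or 18–30 h if the Stage 1 per-protocol window in 6.4 is borrowed; washout of at least one week, 168 h (8.1.9).
- Usual maximum: 48 + 24 = 72 h. With the window: 48 + 18 = 66 h to 48 + 30 = 78 h.
- With washout, if tested at the start of screening: at least 168 + 18 = 186 h to 168 + 30 = 198 h, or 7.75 to 8.25 days.

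**Interval between scheduled tests**

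- Usual: 2 + 14 = 16 days. With washout: at least 7 + 14 = 21 days.
- First capsule (Day 1) to the next scheduled test (Day 14): 13 days.

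**Illustrative new conceptions before the first capsule**

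The documents do not give the share of women of childbearing potential. Assume anywhere from none to all of the 124 randomised, and contraception failing in 1% per year (section 7.1 requires less than this).

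- Over 3 days: 124 × 0.01 × 3/365 = 0.010, so 0 to 0.010.
- Over 8 days: 124 × 0.01 × 8/365 = 0.027, so 0 to 0.027.

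These exclude pregnancies present but undetected at screening, for which the documents give no rate.

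**Per-protocol threshold**

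Section 6.4 drops the per-protocol analysis if fewer than 5% would be excluded. If each missed test counted as ineligibility or a major violation:

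- Of 124 randomised: 6/124 = 4.8%; 7/124 = 5.6%.
- Of the 112 to be evaluated: 5/112 = 4.5%; 6/112 = 5.4%.

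So seven (or six) missed tests alone would cause that analysis to be run.

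**What exclusion 3 means by baseline**

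- Exclusion 12j places it "at the Baseline Visit (Visit 1) within 1.5 hours prior to ketamine infusion", yet Table 3 gives the number Visit 1 to the 24-hour visit.
- Exclusions 12o and 12p equate it with randomisation.
- Section 8.2.1, on ECGs, refers to "the Baseline Visit (at the 24-hour time point".

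The text therefore does not settle whether a pre-infusion test is also intended.

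**The case against.** The requirement has not been dropped. It stands in the synopsis and in section 7.1, section 7.3 insists on full eligibility, and section 14.2 has the Medical Monitor approve the eligibility of screened subjects. Section 8.1 also promises sites a separate document on the order of procedures, which may list the test. All of this stands, and it is why a site *could* miss the test rather than *would*. It does not close the gap. The demand in 8.1.4 that criteria continue to be met applies to entry into Stage 1, before a randomisation test can exist. The Medical Monitor confirmation in 13.8.1 is tied to ketamine responders and mentions no Day 1 pregnancy result.

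The numbers are also modest. The conception figures are tiny even at their upper bound, and they count conceptions rather than pregnancies the added test would detect. Section 8.1.3 speaks of a 24-hour screening period; on that reading the usual screening result is about 24 + 24 = 48 h old, not 72 h. The 8-day case needs a washout extension of unknown frequency. The per-protocol counts are only where the threshold falls, not a forecast. Table 5 lets a missed laboratory test be graded major or minor on the site investigator's opinion, and 112 is the planned evaluable number rather than a defined intent-to-treat count. These points limit the size of the problem but leave the contradiction in place.

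**Conclusion.** The concern holds. The schedule contradicts a binding safety criterion in all three places where test times are given. This is an internal inconsistency; the decision to test at randomisation is right.

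The consequence is a possible first dose without the confirmatory test, relying on a screening result usually up to about 3 days old, or at least about 8 days old after a washout if the test was done at its start. Few pregnancies are likely to be affected, but the number cannot be estimated properly: the documents give neither the share of women of childbearing potential, nor the share needing washout, nor the rate of pregnancies undetected at screening. The primary intent-to-treat analysis, power and type I error are unaffected. Any per-protocol effect depends on how missed tests are graded. The correction should be made because it is cheap and concerns patient safety.

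**What to change.** Add a urine pregnancy test for women of childbearing potential on Day 1, at the 24-hour visit and before the first capsule, to Table 3, Table 4 and section 8.2.1. Keep inclusion 7 and the Day 14 and Day 42 tests as they are.

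Then settle exclusion 3 in both the synopsis and section 7.2. If its baseline is the pre-infusion Day 0 visit, schedule a test there before ketamine as well. If it means randomisation, say so.

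The cost is one mark in Table 3, one entry each in Table 4 and 8.2.1, and one urine test per woman of childbearing potential at a visit that 8.1.6 already requires in person. Clarifying exclusion 3 costs either one further mark and test on Day 0 or a one-word edit where the criterion appears. No endpoint, sample size or analysis changes.

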7.2 Exclusion Criteria

1. Female of childbearing potential who is not willing to use one of the specified forms of birth control during the study.
2. Female that is pregnant or breastfeeding.
3. Female with a positive pregnancy test at screening or baseline.
4. Current diagnosis of a substance use disorder (abuse or dependence, as defined by DSM-5, with the exception of nicotine dependence), at screening or within 6 months prior to screening.
5. Current Axis I disorder, diagnosed at screening with the use of the MINI 7.0.2, that is the primary focus of treatment and BD the secondary focus of treatment for the past 6 months or more.
6. History of schizophrenia or schizoaffective disorders, or any history of psychotic symptoms when not in acute bipolar mood episode.
7. History of anorexia nervosa, bulimia nervosa, or eating disorder not otherwise specified, within 5 years of screening.
8. Any Axis I or Axis II Disorder, which at screening is clinically predominant to their BD or has been predominant to their BD at any time within 6 months prior to screening.
9. Has dementia, delirium, amnestic, or any other cognitive disorder.
10. Has a clinically significant abnormality on the screening physical examination that might affect safety, study participation, or confound interpretation of study results according to the study clinician.
11. Participation in any clinical trial with an investigational drug or device within the past month or concurrent to study participation.
12. Current episode of:
 - i. Hypertension, Stage 1 as defined by a systolic blood pressure ≥ 140 mmHg or diastolic blood pressure ≥ 90 mmHg at screening on two of three measurements at least 15 minutes apart.

-
- j. Hypertension, Stage 1 as defined by a systolic blood pressure ≥ 155 mmHg or diastolic blood pressure ≥ 99 mmHg at the Baseline Visit (Visit 1) within 1.5 hours prior to ketamine infusion on two of three measurements at least 15 minutes apart.
 - k. Recent myocardial infarction (within one year) or a history of myocardial infarction.
 - l. Syncopal event within the past year.
 - m. Congestive heart failure (CHF) New York Heart Association Criteria $>$ Stage 2
 - n. Angina pectoris.
 - o. Heart rate < 50 or > 105 beats per minute at screening or randomization (Baseline Visit).
 - p. QTcF (Fridericia-corrected) ≥ 450 msec at screening or randomization (Baseline Visit).
13. Current history of hypertension, or on antihypertensives for the purpose of lowering blood pressure, with either an increase in antihypertensive dose or increase in the number of antihypertensive drugs used to treat hypertension over the last 2 months.
14. Chronic lung disease excluding asthma.
15. Lifetime history of surgical procedures involving the brain or meninges, encephalitis, meningitis, degenerative central nervous system (CNS) disorder (e.g., Alzheimer's or Parkinson's Disease), epilepsy, mental retardation, or any other disease/procedure/accident/intervention which, according to the screening clinician, is deemed associated with significant injury to or malfunction of the CNS, or history of significant head trauma within the past 2 years.
16. Presents with any of the following lab abnormalities:
- c. Subjects with diabetes mellitus fulfilling any of the following criteria:
 - v. Unstable diabetes mellitus defined as glycosylated hemoglobin (HbA1c) $> 8.5\%$ at screening.
 - vi. Admitted to hospital for treatment of diabetes mellitus or diabetes mellitus-related illness in the past 12 weeks.
 - vii. Not under physician care for diabetes mellitus.
 - viii. Has not been on the same dose of oral hypoglycemic drug(s) and/or diet for the 4 weeks prior to screening. For thiazolidinediones (glitazones) this period should not be less than 8 weeks.
 - d. Any other clinically significant abnormal laboratory result (determined as such by the investigator and medical monitor) at the time of the screening.
17. Any current or past history of any physical condition which in the investigator's opinion might put the subject at risk or interfere with study results interpretation.
18. Positive screening urine test for drugs of abuse at screening: cocaine, amphetamines, barbiturates, opiates.

19. Subjects with exclusionary laboratory values (see Table 2), or requiring treatment with exclusionary concomitant medications (see Appendix 1).
20. Subjects on exclusionary concomitant psychotropic medications.
21. Subjects with a lifetime history of PCP/ketamine drug use.
22. Liver Function Tests higher than 2.5 times upper limit of normal.
23. Known allergies to Lurasidone or Latuda, Cycloserine or Seromycin, Mannitol, Croscarmellose Sodium, Magnesium Stearate, Silicon Dioxide, and/or HPMC (hydroxypropylmethylcellulose).

Table 2 Exclusionary Safety Values of Potential Clinical Concern

Hematology	
Leukocytes	<2 or >17.5 x 10 ³ /mm ³
Platelets	<75 or >700 x 10 ³ /mm ³
Chemistry	
Total bilirubin	>2.5 times the upper limit of the reference range
AST	>2.5 times upper limit of the reference range
ALT	>3 times upper limit of the reference range
GGT	>3 times upper limit of the reference range
Alk Phosphatase	>3 times upper limit of the reference range
Creatinine	>1.3 times upper limit of the reference range
BUN/Urea	>1.3 times upper limit of the reference range
Glucose	<70 mg/dl or >2 times the limits of the reference range
HbA1c	>7.0%
Uric acid	>1.5 times upper limit of the reference range

